6.2 Screening/Baseline

To be completed within four weeks prior to Step 2 of study registration (treatment assignment):

1. Medical history including list of current medications and dosing schedules, history of previous therapies for current disease; and any residual toxicity from prior therapies should be recorded by using the grading schema in CTCAE, v3.0.
2. Zubrod performance status.
3. Baseline tumor measurements
4. Chest x-ray
5. CT/MRI of chest, abdomen and pelvis and/or appropriate imaging. Chest imaging (only in patients with chest disease)
6. Hepatitis screening

To be completed within seven days of initiation of therapy. Therapy must be initiated within 10 calendar days after Step 2 of registration (treatment assignment):

1. Physical exam including pelvic exam
2. Weight
3. Vital signs (blood pressure, pulse, respiratory rate, temperature)
4. Zubrod performance status
5. Complete blood count with leukocyte differential and platelet count
6. Serum chemistries (magnesium, SGPT, total bilirubin, BUN, serum creatinine, glucose and electrolytes).
7. Lipid panel (Triglycerides, LDL, HDL)

6.3 Treatment Evaluations To be obtained every cycle (4 weeks):

1. Weight
2. Complete blood count, serum chemistries (magnesium, SGPT, total bilirubin, BUN, serum creatinine), glucose and electrolytes.
3. Lipid panel (Triglycerides, LDL, HDL)
4. Vital Signs (blood pressure, pulse, respiratory rate, temperature)
5. Physical exam including pelvic exam every cycle if disease is in the pelvis. Otherwise pelvic exam is performed at baseline, after 2 cycles (8 weeks), and then every 3 cycles (12 weeks) thereafter.
6. Zubrod performance status

7. Assessment of treatment related toxicities
8. Hepatitis monitoring, if indicated
9. Medication compliance, pill count

To be obtained after the first 2 cycles (8 weeks):

1. Evaluation of measurable tumor
2. Physical exam (including pelvic exam)
3. CT/MRI scan of chest, abdomen and pelvis and/or appropriate imaging (the same imaging technique used during the initial evaluation will be performed).
Chest imaging (only in patients with chest disease)
4. Assessment of treatment related toxicities

After this first evaluation, patients with progressive disease will be taken off study. To be assigned a status of PR or CR according to RECIST 1.1, tumor measurements must be confirmed by repeat studies (i.e., evaluation of measurable tumor, physical exam, and imaging) that should be performed no less than 4 weeks after the criteria for disease control are first met. To be assigned a status SD, tumor measurements must be confirmed by repeat studies (i.e., evaluation of measurable tumor, physical exam, and imaging) that should be performed no less than 8 weeks after the criteria for disease control are first met.

After these confirmatory studies, to be obtained every 3 cycles (12 weeks):

1. Pelvic exam
2. CT/MRI scan and/or appropriate imaging (the same imaging technique used during the initial evaluation will be performed)
3. Chest imaging (only in patients with chest disease)

6.4 End of Treatment: To be obtained at the end of treatment:

1. Physical exam including pelvic exam
2. Vital signs
3. Zubrod performance status
4. Weight
5. Complete blood count with differential and platelets, serum chemistries (magnesium, SGPT, total bilirubin, BUN, serum creatinine, glucose and electrolytes).
6. Lipid panel (Triglycerides, LDL, HDL)

7. CT/MRI scan of chest, abdomen and pelvis and/or appropriate imaging (the same imaging technique used during the initial evaluation will be performed). Chest imaging (only in patients with chest disease)
8. Assessment of treatment related toxicities
9. Medication compliance/pill count and return of unused medication

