6.1 Schedule of Assessments

Assessments	Screening / baseline	Weekly	Every cycle	Every 2 nd / 3 rd cycle ^d	End of treatment ^j	Follow-up ^h
Medical history	X ^a					
Physical examination	X ^{b,c}		X ^c		X	X
Vital signs	X ^b		X		X	X
Zubrod Performance Status	X ^b		X ^b		X	X
Weight	X ^b		X		X	X
CBC with differential and platelets	X ^b		X		X	
Hepatitis screening/monitoring	X ^{l,n}		X ^{m,o}			
Serum chemistries (Mg+, SGPT, total bilirubin, BUN, serum creatinine/creatinine clearance) and electrolytes, glucose	X ^{b,p}		X		X	
Lipid panel (Triglycerides, LDL, HDL)	X ^b		X		X	
Tumor staging (baseline tumor measurements)	X ^{a,e}					
Chest x-ray	X ^a			X ⁱ	X ⁱ	
CT/MRI of chest, abdomen and pelvis and/or appropriate imaging	X ^{a,e}			X ^f	X ^f	X
Toxicity	X ^a	X ^g	X		X	X
Tumor response				X		
Serum estradiol ^k	X ^a					
Medication compliance/pill count			X ^q			

- a Within 4 weeks prior to Step 2 of study registration (treatment assignment)
- b Within 7 days of initiation of therapy
- c Pelvic exam every cycle if disease is in the pelvis. Otherwise, pelvic exam is done at baseline, after 2 cycles, and then every 3rd cycle thereafter.
- d Obtained after the first two cycles (approximately 8 weeks), after four cycles (approximately 16 weeks) for confirmation, then every three cycles (approximately 12 weeks) thereafter.
- e CT/MRI of chest only in patients with chest disease.
- f Using the same imaging technique used during the initial evaluation.
- g Toxicity will be assessed on an ongoing basis.
- h Follow-up time interval at the physician's discretion. Follow up begins after the patient stops study medication.
- i Only in patients with chest disease
- j Within 4 weeks of the last dose of study drug.
- k Documentation of a serum estradiol < 10 pg/mL is required only for patients in whom hysterectomy was performed premenopausally and in whom bilateral oophorectomy was not completed. Estradiol is not required for women known to be menopausal or surgically castrated.
- l Hepatitis B Virus testing: Prior to randomization (or starting study drug in non-randomized trials), the categories of patients listed in Section 3.2 should be tested for hepatitis B serologic markers and viral load: HBV-DNA HBsAg, HBc Ab, and HBs Ab.
- m HBV DNA monitoring should be done depending on results from serologic markers and viral load as listed in Table 3-3.

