7.1.1 Definitions

Evaluable for toxicity. All patients will be evaluable for toxicity from the time of their first treatment with Letrozole (Evirolimus) and RAD001.

Evaluable for objective response. Only those patients who have measurable disease present at baseline, have received at least one cycle of therapy, and have had their disease re-evaluated will be considered evaluable for response. These patients will have their response classified according to the definitions stated below. (Note: Patients who exhibit objective disease progression prior to the end of cycle 1 will also be considered evaluable.)

Evaluable Non-Target Disease Response. Patients who have lesions present at baseline that are evaluable but do not meet the definitions of measurable disease, have received at least one cycle of therapy, and have had their disease re-evaluated will be considered evaluable for non-target disease. The response assessment is based on the presence, absence, or unequivocal progression of the lesions.

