7.1.4.3 Evaluation of Best Overall Response

The best overall response is the best response recorded from the start of the treatment until disease progression/recurrence (taking as reference for progressive disease the smallest measurements recorded since the treatment started). The patient's best response assignment will depend on the achievement of both measurement and confirmation criteria.

For Patients with Measurable Disease (i.e., Target Disease)

Target Lesions	Non-Target Lesions	New Lesions	Overall Response	Best Overall Response when Confirmation is Required*
CR	CR	No	CR	≥4 wks. Confirmation**
CR	Non-CR/Non-PD	No	PR	≥4 wks. Confirmation**
CR	Not evaluated	No	PR	
PR	Non-CR/Non-PD/not evaluated	No	PR	
SD	Non-CR/Non-PD/not evaluated	No	SD	documented at least once ≥4 wks. from baseline**
PD	Any	Yes or No	PD	no prior SD, PR or CR
Any	PD***	Yes or No	PD	
Any	Any	Yes	PD	

* See RECIST 1.1 manuscript for further details on what is evidence of a new lesion.

** Only for non-randomized trials with response as primary endpoint.

*** In exceptional circumstances, unequivocal progression in non-target lesions may be accepted as disease progression.

Note: Patients with a global deterioration of health status requiring discontinuation of treatment without objective evidence of disease progression at that time should be reported as “*symptomatic deterioration*.” Every effort should be made to document the objective progression even after discontinuation of treatment.

For Patients with Non-Measurable Disease (i.e., Non-Target Disease)

Non-Target Lesions	New Lesions	Overall Response
CR	No	CR
Non-CR/non-PD	No	Non-CR/non-PD*
Not all evaluated	No	not evaluated
Unequivocal PD	Yes or No	PD
Any	Yes	PD

* ‘Non-CR/non-PD’ is preferred over ‘stable disease’ for non-target disease since SD is increasingly used as an endpoint for assessment of efficacy in some trials so to assign this category when no lesions can be measured is not advised

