10 STATISTICAL METHODOLOGY

This is a phase II activity trial. We will accrue a minimum of 10 patients and a maximum of 35 evaluable patients at a rate of 2 patients per month. We estimate 7 patients will be inevaluable and thus need to be replaced. Therefore our total number of patients will not exceed 42. The primary outcome for this trial is the objective response or stable disease rate (CR + PR + SD), which is evaluated within approximately 8 weeks of treatment. A confirmatory evaluation will be made no sooner than 4 weeks from this event (8 weeks, if SD). Once a response category is confirmed, evaluation for objective responses will be made every 12 weeks as outlined in Sections 6 and 7.1.3. Our target objective response or stable disease rate is 20%. We will monitor the objective response or stable disease rate as patients accrue and are evaluated following the example of Thall and Simon.[17] We will stop the trial if we have evidence that the target objective response or stable disease rate cannot be met.

We will stop the trial early if $P(\text{objective response or stable disease rate} \geq 20\% \mid \text{data from the trial}) < 0.10$. That is, given the outcomes from the patients who have already been evaluated, if we determine that there is less than a 10% chance that the objective response or stable disease rate is 20% or more, we will stop the trial. This decision rule gives the following stopping rule. We assume a uniform prior distribution for the rate of objective response or stable disease. Stop the trial if: $[\# \text{ of patients with objective response or stable disease} / \# \text{ of patients evaluated}] < 1/10, 2/17, 3/24, 4/31$.

The operating characteristics of this study design are shown in the following table.

Operating Characteristics of Monitoring Rule				
Rate of CR + PR + SD	Probability of Stopping Early	P ₂₅	P ₅₀	P ₇₅
0.05	0.956	10	10	17
0.10	0.725	10	17	35
0.15	0.436	17	35	35
0.20	0.220	35	35	35
0.25	0.097	35	35	35

We will estimate the rate OF CR + PR + SD with a 90% credible interval once the study is complete. If we complete the study with 11 patients with treatment success (CR or PR or SD) among 35 patients total (31%), then our 90% credible interval for the success rate would be 20.5 to 45.5%.

We will also estimate the overall survival and progression free survival for patients on study with the product-limit estimator of Kaplan and Meier (1958). [18]

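### The best-overall-response table in 7.1.4.3 accepts stable disease on one scan at least 4 weeks from baseline, while 6.3 and section 10 require confirmation at least 8 weeks later; section 10 does not say which status the interim looks count

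*Combined protocol and SAP*

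**What the plan says.** Section 10 makes the primary outcome the rate of CR, PR or SD, "which is evaluated within approximately 8 weeks of treatment". It then adds: "A confirmatory evaluation will be made no sooner than 4 weeks from this event (8 weeks, if SD"). The stopping rule divides patients with response or SD by patients evaluated. The final estimate is the CR+PR+SD rate with a 90% credible interval. Neither is expressly tied to confirmed or first-scan status.

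Section 6.3 makes confirmation a condition of the status itself. CR and PR need repeat studies at least 4 weeks later, and SD needs repeat studies "performed no less than 8 weeks after the criteria for disease control are first met". Footnote d in 6.1 schedules imaging after two cycles and again "after four cycles (approximately 16 weeks) for confirmation".

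The best-overall-response table in 7.1.4.3 has a different SD entry: "documented at least once ≥4 wks. from baseline". The footnote attached to that entry reads "Only for non-randomized trials with response as primary endpoint". This trial has a single arm, and response including SD is its primary endpoint, so the footnote brings the entry into force here.

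On evaluability, 7.1.1 says that patients with measurable disease who have had at least one cycle and "have had their disease re-evaluated will be considered evaluable for response". Section 10.1 makes patients who stop for reasons other than progression, before a response is established, evaluable for toxicity only.

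**The concern.** Two SD rules apply to the same primary endpoint. With the first scan at about week 8, the 7.1.4.3 entry is met by that scan alone, while 6.3 needs the week-16 scan as well. The rules disagree on any patient who is stable at week 8 and has progressed by week 16.

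These patients may not be few. The earlier single-agent trial described in section 1.5 saw no objective responses; all its clinical benefit was SD. If SD again supplies most successes, the choice of rule moves the headline rate. If the interim looks use one status and the final rate the other, the operating-characteristics table describes only one of them.

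**Working it through.** **1. The rules side by side.**

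| Place | What SD needs |
|---|---|
| 6.3 | Repeat studies at least 8 weeks after SD criteria are first met |
| Section 10 | Confirmatory evaluation no sooner than 8 weeks after the first |
| 6.1, footnote d | Week-16 scan, scheduled for confirmation |
| 7.1.4.3 table | One documentation, at least 4 weeks from baseline |

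Three places agree and one does not. SD at week 8 with progression at week 16 is best response SD in the last row and cannot be assigned SD under the first.

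**2. The plan's own figures.** Inputs from section 10: uniform prior, target 20%, stop if the posterior probability of a rate of at least 20% is below 0.10, boundaries <1/10, <2/17, <3/24, <4/31, maximum 35.

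- Boundaries: with x successes in n, the posterior is Beta(1+x, 1+n−x). P(rate ≥ 20%) is 0.086 at 0/10, 0.099 at 1/17, 0.098 at 2/24 and 0.093 at 3/31, all below 0.10.
- Early stopping: exact binomial recursion over the four looks, at true rates 0.05/0.10/0.15/0.20/0.25, gives 0.955/0.723/0.432/0.220/0.101. The plan prints 0.956/0.725/0.436/0.220/0.097.
- Final interval: 11/35 gives Beta(12, 25), with 5th and 95th percentiles 20.5% and 45.5%, as printed.

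The arithmetic reproduces. What is open is which SD status feeds it.

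**3. Illustration from the single-agent trial (section 1.5).** Observed 12/28 = 42.9%, all SD. Assume this was a single-scan rate. Let f be the assumed share of week-8 SD still stable at confirmation; the documents give no value. Confirmed rate = 0.429 × f.

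| f | Confirmed rate | P(stop early) |
|---|---|---|
| 1 (single-scan) | 42.9% | 0.4% |
| 0.8 | 34.3% | 2.1% |
| 0.6 | 25.7% | 9.0% |
| 0.5 | 21.4% | 17.8% |
| 0.4 | 17.1% | 32.9% |

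For 35 evaluable patients, 42.9% is 15 successes. Beta(x+1, 36−x) gives these 90% credible intervals:

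- 15/35: 30.2% to 56.7%
- 15 × 0.8 = 12/35: 22.9% to 48.3%
- 15 × 0.4 = 6/35: 9.5% to 30.3%

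**4. Illustration from the other mTOR-inhibitor trial (section 1.5).** 25% PR and 57% SD, in patients without prior chemotherapy. Keep all PRs and half the SD: 25 + 0.5 × 57 = 53.5%. The same recursion gives early stopping of 0.05%. With no SD retained the rate is 25%, and early stopping is about 10%.

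**5. Delay if the looks wait for confirmation.** 8 weeks × 12/52 = 1.85 months; at 2 patients per month, 3.7, or about 4 patients.

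**The case against.** The strongest reply is that the plan already resolves the conflict. Section 6.3 conditions SD status on confirmation, so counting SD patients naturally means counting confirmed ones. Section 10 speaks of later evaluations once a response category has been confirmed. The text introducing the 7.1.4.3 table says that best response depends on both measurement and confirmation criteria. On this view one table cell is wrong and nothing else.

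Much of that stands. A reader might infer that the final primary rate has no definition at all; the documents do not support this, since the weight of the text favours confirmed status. But the SD entry is the table's own confirmation criterion, so the general sentence above it does not override it. Section 10 also places the outcome at about 8 weeks, leaving the interim numerator and the handling of patients awaiting confirmation unstated.

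A reader might also infer that trial conduct would change greatly, from 0.4% to 18% or more early stopping. That contrast needs an assumed retention share, needs the 43% to have been single-scan, and carries over a single-agent result in chemotherapy-refractory patients. This trial admits patients with no prior chemotherapy and adds letrozole. Starting from the other mTOR-inhibitor trial, the effect on stopping is negligible at 50% retention. The aromatase-inhibitor trial in section 1.2 (2 PR and 2 short-term SD in 23 patients, 4/23 = 17%) points lower. The documents do not settle where this trial falls.

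Finally, patients with week-8 SD who leave before confirmation might be read as a source of bias. They are evaluable under 7.1.1 and excluded under 10.1 only if establishing response means confirmed status. Section 10 already allows for this kind of loss: "We estimate 7 patients will be inevaluable and thus need to be replaced". This is a secondary matter of consistency.

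**Conclusion.** The contradiction is real and concerns the primary endpoint. The 7.1.4.3 SD entry conflicts with 6.3, section 10 and the schedule, and its footnote makes it apply to this trial. The conclusion rests on the text alone and needs none of the assumed numbers.

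Confirmed status is the better-supported reading for the final rate. For the interim looks, the plan does not say which status is counted or how patients awaiting confirmation enter the denominator.

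The size is uncertain. Any patient with SD at week 8 and progression at week 16 changes the reported rate. The effect on early stopping runs from negligible to substantial, depending on the starting rate and on a retention share that the documents do not give. The stopping rule and the credible-interval calculation are themselves sound. This should be fixed, as a clarification of the endpoint rather than a redesign.

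**What to change.** - In 7.1.4.3, change the SD entry to match 6.3 and section 10.
- In section 10, state that the final CR+PR+SD rate uses confirmed status, so that SD at week 8 followed by progression at the confirmatory scan is a failure.
- In section 10, state which status the interim looks use and how patients awaiting confirmation are counted. Either status can be defended. With confirmed status, each look waits up to about 8 weeks, during which about 4 more patients enrol. With first-scan status, the operating-characteristics table should be read at the week-8 rate.
- While editing, make 7.1.1 and 10.1 consistent on patients with week-8 SD who leave before confirmation. Whether they stay in the denominator or are replaced is the sponsor's choice.

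The cost is wording only. The scans after cycles 2 and 4 are already scheduled. The downside is a lower headline rate than single-scan SD would give.

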6.5 Follow-up

Follow-up will be at the discretion of the patient's primary physician. However, follow-up data will be due to M. D. Anderson OMCR every 6 months.

To be obtained during follow-up visits:

- Physical exam including pelvic exam
- Vital signs (blood pressure, pulse, respiratory rate, temperature, weight)
- Performance status
- CT/MRI scan of chest, abdomen and pelvis and/or appropriate imaging (the same imaging technique used during the initial evaluation will be performed). Chest imaging (only in patients with chest disease). The frequency of imaging will be determined by the physician.
- Toxicity assessment

6.6 Correlative Studies

When available, we will collect paraffin embedded tumors from the original tumor at the time of hysterectomy, pretreatment biopsy, and post-treatment biopsy. We will evaluate the immunohistochemical expression of PTEN, mTOR, AKT, p70S6K, and E4-BP1 using commercially available antibodies. We will also evaluate the difference in expression of these proteins between the primary tumors and the recurrences (pre- and post- treatment) in the same patients to determine if there are any alterations of the expression of these biomarkers during the progression of disease. Paraffin blocks will be requested from all study participants (both responders and non-responders). If paraffin blocks are not available, at least 5 slides each (pre- and post-treatment) will be requested. Pre-treatment samples will be sequenced to analyze the mutational status of K-Ras as this may also be a marker of response.

7 Efficacy and Safety Assessments – RECIST 1.1

7.1 Antitumor Effect – Solid Tumors

For the purposes of this study, patients should be re-evaluated for response **after the first 2 cycles (8 weeks)**. In addition to a baseline scan, confirmatory scans should also be obtained **after the next two cycles (8 weeks)** following **initial documentation of objective response**.

Response and progression will be evaluated in this study using the new international criteria proposed by the revised Response Evaluation Criteria in Solid Tumors (RECIST) guideline (version 1.1) [*Eur J Ca* 45:228-247, 2009]. Changes in the largest diameter (unidimensional measurement) of the tumor lesions and the shortest diameter in the case of malignant lymph nodes are used in the RECIST criteria.

7.1.1 Definitions

Evaluable for toxicity. All patients will be evaluable for toxicity from the time of their first treatment with Letrozole (Evirolimus) and RAD001.

Evaluable for objective response. Only those patients who have measurable disease present at baseline, have received at least one cycle of therapy, and have had their disease re-evaluated will be considered evaluable for response. These patients will have their response classified according to the definitions stated below. (Note: Patients who exhibit objective disease progression prior to the end of cycle 1 will also be considered evaluable.)

Evaluable Non-Target Disease Response. Patients who have lesions present at baseline that are evaluable but do not meet the definitions of measurable disease, have received at least one cycle of therapy, and have had their disease re-evaluated will be considered evaluable for non-target disease. The response assessment is based on the presence, absence, or unequivocal progression of the lesions.

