10.1 Definition of Populations for Analyses

Patients who are removed from the study during the first course because of progression are considered evaluable for efficacy only if progression can be documented per RECIST 1.1 criteria. Patients who come off

treatment for reasons other than progression (and prior to establishing response) are evaluable for toxicity only.

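### Sections 7.1.1 and 10.1 disagree on whether a re-evaluated patient who stops for a reason other than progression, before response is established, counts in the primary denominator

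*Combined protocol and SAP*

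**What the plan says.** The primary endpoint is a proportion: "The primary outcome for this trial is the objective response or stable disease rate (CR + PR + SD"), assessed at about 8 weeks (Section 10). Section 10 plans for at most 35 evaluable patients, expects 7 inevaluable patients to be replaced, and caps the total at 42.

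Two sections say who is evaluable.

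- Section 7.1.1 requires measurable disease at baseline and asks that patients "have received at least one cycle of therapy, and have had their disease re-evaluated will be considered evaluable for response". It adds that their response will be classified. The reason for stopping plays no part. It also states: "Patients who exhibit objective disease progression prior to the end of cycle 1 will also be considered evaluable".
- Section 10.1 says that patients who come off "treatment for reasons other than progression (and prior to establishing response) are evaluable for toxicity only". It has two tests, the reason for stopping and whether response had been established.

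The plan does not define establishing response. Section 10 says "A confirmatory evaluation will be made no sooner than 4 weeks from this event (8 weeks, if SD"), and Section 6.3 says "To be assigned a status SD, tumor measurements must be confirmed by repeat studies", at least 8 weeks after the criteria are first met. The best-response table in 7.1.4.3 instead accepts SD "documented at least once ≥4 wks. from baseline".

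The first scheduled scan comes after cycle 2, at about week 8 (5.2.6 and 6.3). Section 6.4 also requires imaging at the end of treatment: "CT/MRI scan of chest, abdomen and pelvis and/or appropriate imaging (the same imaging technique used during the initial evaluation will be performed"). The schedule in 6.1 places that visit within 4 weeks of the last dose.

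**The concern.** Take a patient who completes cycle 1, stops in week 5 or 6 because of toxicity or refusal, and has her end-of-treatment scan. She has measurable disease, one cycle and a re-evaluation, so 7.1.1 puts her in the response denominator and classifies her. She stopped for a reason other than progression and had no on-treatment scan, so 10.1 makes her toxicity-only and Section 10 allows her to be replaced. Read literally, 10.1 does this even when the scan shows RECIST progression, because progression was not why she stopped.

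This is a single-arm trial monitored on a posterior probability, so the denominator is part of the decision rule. Two people applying the plan to the same data could report different rates, count different numbers of replacements and reach different stopping decisions. Under 10.1, the patients removed have been treated and scanned and have no confirmed success, so dropping them tends to raise the rate.

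**Working it through.** **Who is in dispute**

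| Patient | 7.1.1 | 10.1 |
|---|---|---|
| Documented progression during cycle 1 | evaluable | evaluable |
| Established CR, PR or SD, later stops for toxicity | evaluable | evaluable |
| Stops after cycle 1 and before week 8, not for progression; first imaged at end of treatment | evaluable | toxicity only |
| SD at week 8, stops before confirmation, not for progression | evaluable | toxicity only if establishing means confirmed; evaluable if one on-treatment scan is enough |

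The third row is in conflict even if a single on-treatment scan is enough to establish response, because she had none. The fourth row depends on the undefined term.

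**Inputs (Section 10).** Uniform prior; target 20%; stop if the posterior P(rate ≥ 20%) is below 0.10; maximum 35 evaluable; example 11/35. With s successes among n patients, the posterior is Beta(1+s, 1+n−s).

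**The plan's own figures first**

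- 11/35 gives Beta(12, 25), with a 90% interval of 20.5 to 45.5%, as stated.
- P(rate ≥ 20%) is 0.086 at 0/10, 0.099 at 1/17, 0.098 at 2/24 and 0.093 at 3/31. All four boundaries reproduce.
- Exact early-stopping probabilities at true rates 0.05, 0.10, 0.15, 0.20 and 0.25 are 0.955, 0.723, 0.432, 0.220 and 0.101. The plan prints 0.956, 0.725, 0.436, 0.220 and 0.097.

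**Effect on the final rate.** Let k be the number of patients evaluable under 7.1.1 but excluded under 10.1. The documents do not give k. I assume 0 to 7, taking the range from the 7 expected inevaluable patients. Suppose the trial accrues 11/35 under 10.1 and the k patients are then added as non-successes, giving 11/(35+k):

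| k | Rate | 90% interval | P(rate ≥ 20%) |
|---|---|---|---|
| 0 | 11/35 = 31.4% | 20.5–45.5% | 0.958 |
| 1 | 11/36 = 30.6% | 19.9–44.4% | 0.948 |
| 4 | 11/39 = 28.2% | 18.3–41.4% | 0.913 |
| 7 | 11/42 = 26.2% | 17.0–38.8% | 0.864 |

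A denominator above 35 arises only in this re-analysis. If 7.1.1 governed from the start, these patients would not be replaced and accrual would end at 35 evaluable. For k = 7 the expected count is 11 × 35/42 = 9.2, so about 9/35 = 25.7% (15.9–39.6%).

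**Effect on stopping.** If the true rate is 20% in the 10.1 set and the k patients are non-successes spread evenly over accrual, the rate in the 7.1.1 set is 0.20 × 35/(35+k):

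| k | Rate under 7.1.1 | P(stop early) |
|---|---|---|
| 0 | 20.0% | 0.22 |
| 1 | 19.4% | 0.24 |
| 2 | 18.9% | 0.26 |
| 4 | 17.9% | 0.29 |
| 7 | 16.7% | 0.35 |

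One patient can change an interim decision. At 1/16 the posterior probability is 0.118 and the trial continues. One more disputed non-success makes it 1/17, the probability is 0.099, and the trial stops.

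**The case against.** The strongest reply is that 10.1 is the section that defines analysis populations and sits with the stopping rule, while 7.1.1 belongs to the RECIST assessment rules and could be read as a minimum condition that 10.1 narrows. That gives a reader grounds to use 10.1. But there is no precedence clause, and the reading does not account for the statement in 7.1.1 that these patients will have their response classified.

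The second reply is that the conflict is small. If the first on-treatment scan establishes response, only patients first imaged after stopping remain in dispute. The 7 expected inevaluable patients also include any with less than one cycle or no scan. Both points stand: k may be 0, 1 or 2. Because 7 is itself an estimate, it is not a strict upper bound either.

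Third, letting 7.1.1 govern is one of several defensible rules, and it still replaces patients who stop before a full cycle without documented progression, or who are never re-evaluated. That is fair, but it is no reason to leave two rules in force.

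Two stronger readings are tempting and are not supported. A reader might infer that 10.1 excludes everyone who stops for a reason other than progression; its qualifier about establishing response rules that out. A reader might also infer that counting the disputed patients as SD could lift the rate to 18/42 = 42.9%; Sections 6.3 and 10 require SD to be confirmed 8 weeks later, and only the looser table in 7.1.4.3 would permit that figure.

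**Conclusion.** The inconsistency is real but limited to patients who meet 7.1.1, stop for a reason other than progression, and have no established response. Its extent turns on the undefined term. The direction of concern is upward bias in the primary rate if 10.1 is followed. On the plan's example the rate under 7.1.1 would be lower by 0.9 points at k = 1 (31.4% to 30.6% after rounding) and by about 5 points at k = 7, with the lower credible limit below 20% from k = 1. These sizes rest on an assumed k of 0 to 7 and on counting every disputed patient as a non-success. The design calculations in Section 10 reproduce and are not in question. The point should be settled before data are analysed; it does not undermine the design.

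**What to change.** Replace the last sentence of 10.1 with a rule to this effect:

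- Any patient who meets 7.1.1, including by way of the end-of-treatment scan, stays in the efficacy denominator whatever her reason for stopping.
- Progression on that scan is a failure.
- A patient without CR, PR or SD confirmed as 6.3 requires is not counted as a success.
- Only patients who do not meet 7.1.1 are inevaluable and replaced.

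Define establishing response as confirmed under 6.3, and reconcile the SD entry in the 7.1.4.3 table with that definition. State that the same set is used for the stopping rule, the replacement count and the final credible interval.

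This costs one paragraph of wording and a correction to one table. It needs no extra patients or scans and does not touch treatment decisions. The reported rate may be a few points lower, and early stopping somewhat more likely, than under 10.1.
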